2.3.2 Benefit Assessment

This is the first study in pediatric participants so the benefits of AZD7442 in prophylaxis and treatment of COVID-19 in pediatrics is unknown. In both the PROVENT and STORM CHASER trials in adults, AZD7442 reduced the risk of developing symptomatic COVID-19 by more than 70% compared with placebo in participants who were SARS-CoV-2 negative at baseline (see Section 2). In the TACKLE study (NCT04723394), AZD7442 reduced the risk of developing severe COVID-19 or death by 50% compared to placebo in non-hospitalized adults who had been symptomatic for 7 days or less, and the risk was reduced by 67% if participants were treated within 5 days of symptom onset. Importantly, 90% of trial participants were from populations at high risk for progressing to severe COVID-19. Additional adult studies for the treatment of mild to moderate COVID-19 and severe COVID-19 with AZD7442 are ongoing.

The FDA has authorized for emergency use under an EUA, AZD7442 as EVUSHELD (tixagevimab and cilgavimab administered together) for the pre-exposure prophylaxis of COVID-19 in adults and children (≥ 12 years weighing at least 40 kg) who are moderately to severely immunocompromised due to an underlying immune disease or are taking immunosuppressive medications and therefore unable to mount an adequate immune response to COVID-19 vaccine. In addition, use is authorized in those with a history of severe adverse reaction to a COVID-19 vaccine, in whom COVID-19 vaccine is not recommended.

Despite the rollout of effective SARS-CoV-2 vaccines, a sizeable proportion of the general population remain unprotected and many young children are ineligible to receive a vaccine. There remains a clear unmet medical need to neutralize SARS-CoV-2 and ensure protection against emerging variants, particularly in those individuals not expected to mount an adequate response to complete active immunization (CDC 2021c), and those for whom vaccination is not suitable. AZD7442 remains the only prophylactic mAb to successfully neutralize the Omicron variant authentic virus (BA.1) in vitro (VanBlargan et al 2022).

Recruitment will target pediatric participants aged \geq 29 weeks GA to $<$ 18 years who are likely to benefit from prophylaxis or treatment with AZD7442 because they either have severe COVID-19 or an underlying condition that increases their risk of developing severe COVID-19.

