4.2.1 Rationale for Choice of Endpoints

The endpoints chosen for this Phase I PK/PD and safety study are consistent with those in AZD7442 studies in adults.

The primary study PK endpoints are those required to characterize the PK profile of AZD7442 following a single IM or IV dose administered to pediatrics aged \geq 29 weeks GA to < 18 years (Day 1 through Day 366). Pharmacokinetic sampling will be kept to a minimum due to the age of the population under study: one sample on Day 1 for participants receiving an IV infusion, one sample during the first 2 weeks for all participants (at either Day 4, 8, 11, or 15, spread across participants), then one sample at Day 31, 92, 183, and 366 (ie, the total number of samples per participant is up to 5 samples for IM administration and 6 samples for IV administration due to the additional sample taken at the end of the infusion on Day 1). Pharmacokinetic data will be analyzed by population methods and if data permit by non-compartmental analysis approach. This sampling scheme also enables serum AZD7442 concentration data to be obtained at the time points of primary efficacy endpoint evaluation for prophylaxis and treatment in the adult program. Pharmacokinetic profiles of AZD7442 are expected to be similar across the prophylaxis and treatment populations recruited because AZD7442 is cleared via nonspecific intracellular metabolism and will not be affected by binding to the exogenous target SARS-CoV-2. Therefore, PK data will be pooled across the cohorts within each age group.

The PD markers that are measured in this PK/PD and safety study will be used to support the assumption that the exposure-response relationship is similar for adults and children. In SARS-CoV-2 infected and non-infected children, the SARS-CoV-2 neutralizing antibody titer will be measured in a validated live neutralization assay. In addition, the neutralizing antibody titer will be correlated to the serum AZD7442 concentration. The correlation between drug level and neutralizing antibody titer in children will be compared to the correlation derived in adult serum samples.

The measures of viral load, disease progression or recovery, SARS-CoV-2 infections, and COVID-19-related death mirror the endpoints in the adult studies with AZD7442.

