8.1 Efficacy Assessments

8.1.1 Monitoring COVID-19 Symptoms

Progression of COVID-19 will be captured and recorded in the eCRF.

To determine the incidence of infection in Cohort 1, when a participant develops at least one of the COVID-19 qualifying symptoms listed in [Table 13](#) after Day 1, the participant, his/her caretaker, or his/her legal representative must contact the study site. A sample will be collected for SARS-CoV-2 RT-PCR to confirm the participant is positive (see Section [8.6.1](#)). COVID-19 qualifying symptom(s), SARS-CoV-2 positive test results, and/or COVID-19 diagnosis will be collected and recorded in the eCRF as AEs.

In Cohorts 2 and 3, COVID-19 symptoms or signs listed in [Table 13](#) will only be recorded as

AEs when any of the following occur:

- The sign or symptom is serious according to the definition in Appendix B 2.
- The participant discontinues the study due to the sign or symptom.
- In the Investigator's judgment, the sign or symptom is not considered COVID-19 related.

Table 13 COVID-19 Qualifying Symptoms

Participant must present with at least one of the following symptoms:	
Duration	Symptom
No minimum duration	Fever
	Shortness of breath
	Difficulty breathing
Must be present for \geq 2 days	Chills
	Cough
	Fatigue
	Muscle aches
	Body aches
	Headache
	New loss of taste
	New loss of smell
	Sore throat
	Congestion
	Runny nose
	Nausea
	Vomiting
	Diarrhea
	Abdominal pain
	Poor appetite/feeding problems

CDC, Centers for Disease Control and Prevention; COVID-19, coronavirus disease 2019.

Adapted from [CDC 2020](#).

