8.1.2 Severe COVID-19 Criteria

In all cohorts, severe COVID-19 will be characterized by a minimum of either pneumonia (fever, cough, tachypnea, or dyspnea, and lung infiltrates) or hypoxemia ($\text{SpO}_2 < 90\%$ in room air and/or severe respiratory distress) and a WHO Clinical Progression Scale score of 5 or higher ([Table 14](#)). Severe COVID-19 will be collected and recorded in the eCRF as an SAE.

Table 14 WHO Clinical Progression Scale

Patient state	Descriptor	Score
Uninfected	Uninfected, no viral RNA detected	0
Ambulatory mild disease	Asymptomatic; viral RNA detected	1
	Symptomatic; independent	2
	Symptomatic; assistance needed	3
Hospitalized: moderate disease	Hospitalized; no oxygen therapy ^a	4
	Hospitalized; oxygen by mask or nasal prongs	5
Hospitalized: Severe Disease	Hospitalized; oxygen by NIV or high flow	6
	Intubation and mechanical ventilation, $pO_2/FiO_2 \geq 150$ or $SpO_2/FiO_2 \geq 200$	7
	Mechanical ventilation $pO_2/FiO_2 < 150$ ($SpO_2/FiO_2 < 200$) or vasopressors	8
	Mechanical ventilation $pO_2/FiO_2 < 150$ and vasopressors, dialysis, or ECMO	9
Dead	Death	10

^a If hospitalized for isolation only, record status as for ambulatory patient.

ECMO, extracorporeal membrane oxygenation; FiO_2 , fraction of inspired oxygen; NIV, non-invasive ventilation; pO_2 , partial pressure of oxygen; SpO_2 , oxygen saturation, WHO, World Health Organization.
(Marshall et al 2020)

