##### **4.2.5.2 Progression of COVID-19**

To evaluate the proportion of participants with progression of COVID-19 after a single IM or IV dose of AZD7442 in pediatric participants, the count and percentage of participants in the SAF with worsening of COVID-19 will be determined by occurrence of an increase in symptom severity (reported through AEs and the weekly contact) one or more new symptoms (reported through AEs and the weekly contact) or hospitalization or death related to COVID-19 up to day 29 (inclusive). The summary will be tabulated by cohort.

The time to (first) progression [date of AE – date of Day 1 +1] will also be listed and summarized via n, median, 1st and 3rd quartile, minimum, and maximum by weight categories, dose, and route of administration for the SAF.

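### The SAP's COVID-19 progression endpoint has no relatedness condition on symptoms, so under the protocol's AE rule it is misclassified; it also pools mild symptoms with hospitalisation and death

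*SAP*

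**What the plan says.** **Definition.** The protocol lists the proportion with progression through Day 29 as a secondary endpoint for Cohorts 2 and 3 (section 3, Table 4) but does not define progression. SAP 4.2.5.2 does. Worsening is "determined by occurrence of an increase in symptom severity (reported through AEs and the weekly contact"), or "one or more new symptoms (reported through AEs and the weekly contact) or hospitalization or death related to COVID-19 up to day 29 (inclusive"). Relatedness to COVID-19 is mentioned only at the hospitalisation and death end of that sentence.

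**Timing.** The same section adds: "The time to (first) progression [date of AE – date of Day 1 +1] will also be listed and summarized".

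**What becomes an AE.** Protocol 8.1.1 restricts AE recording of symptoms in the treatment cohorts. The rule opens "In Cohorts 2 and 3, COVID-19 symptoms or signs listed in" Table 13, and gives three conditions, any one of which makes the symptom an AE: it is serious, the participant leaves the study because of it, or "In the Investigator's judgment, the sign or symptom is not considered COVID-19 related".

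**Weekly contact.** The Schedule of Activities footnotes (protocol Tables 2 and 3) have the investigator ask each week about AEs and, separately, about COVID-19 symptoms over the preceding week.

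**Severe disease and adults.** Protocol 8.1.2 says "In all cohorts, severe COVID-19 will be characterized by a minimum of either pneumonia" or hypoxaemia, with a WHO Clinical Progression Scale score of at least 5, and records it as an SAE. The progression definition does not use it. Protocol 4.2.1 states: "The measures of viral load, disease progression or recovery, SARS-CoV-2 infections, and COVID-19-related death mirror the endpoints in the adult studies with AZD7442". The adult outpatient treatment result is described in protocol 2.3.2 as "AZD7442 reduced the risk of developing severe COVID-19 or death by 50% compared to placebo in non-hospitalized adults".

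**The concern.** The AE rule is sensible for safety reporting: it keeps the expected symptoms of the disease under treatment out of the AE tables. The difficulty comes when the SAP reuses those AE data to measure the disease. For non-serious symptoms that do not end participation, the rule leaves in the AE data exactly the symptoms that are not COVID-19 and removes those that are. A definition that accepts symptom AEs without a relatedness condition can therefore count ruled-out symptoms as progression and, if driven by AE records, miss true worsening.

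A second problem is that one mild new symptom and a COVID-19 death carry equal weight in a single percentage, with no breakdown by component. A reader of the study report could not tell which of these the figure describes.

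**Working it through.** The plan gives no expected rate, precision or power for this endpoint, so there is no figure to reproduce. The check compares the texts and then works out the direction of error.

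**Step 1. Which symptoms reach which source (Cohort 2, Table 13 symptoms, protocol 8.1.1)**

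| Symptom | AE record? | Weekly contact? | AE date? |
|---|---|---|---|
| Serious, or ends participation | Yes | Possible | Yes |
| Non-serious, stays in study, judged not COVID-19 | Yes | Possible | Yes |
| Non-serious, stays in study, COVID-19 related | No | Only route | No |

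The second row is counted under the SAP wording although it is not COVID-19. The third row is what the endpoint should capture, and it has no date under the SAP's time-to-progression formula.

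**Step 2. Direction of error, with no assumed rates**

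Let S be children with COVID-19 hospitalisation or death, C those with non-serious COVID-19-related worsening as captured at the weekly contact, and U those with a symptom AE judged not COVID-19 related. Serious or discontinuing COVID-19 symptoms can be added to S without changing the argument. The target is S or C.

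- Either source counts: the numerator is S or C or U. It contains the target, so the proportion equals or exceeds it.
- AE-driven count: the numerator is S or U. It gains children who are only in U and loses children who are only in C. The sign depends on which group is larger.

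**Step 3. Illustration with assumed rates**

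The rates s, c and u are assumptions, taken as independent; none comes from the documents. Here s = 5%, c = 20% or 50%, u = 0%, 10% or 30%.

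- Target: 1 − (1 − s)(1 − c)
- Either source: 1 − (1 − s)(1 − c)(1 − u)
- AE-driven: 1 − (1 − s)(1 − u)

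| c | u | Target | Either source | AE-driven |
|---|---|---|---|---|
| 20% | 0% | 24.0% | 24.0% | 5.0% |
| 20% | 10% | 24.0% | 31.6% | 14.5% |
| 20% | 30% | 24.0% | 46.8% | 33.5% |
| 50% | 0% | 52.5% | 52.5% | 5.0% |
| 50% | 10% | 52.5% | 57.25% | 14.5% |
| 50% | 30% | 52.5% | 66.75% | 33.5% |

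For example, at c = 20% and u = 10%, the either-source value is 1 − 0.95 × 0.80 × 0.90 = 31.6%, and the AE-driven value is 1 − 0.95 × 0.90 = 14.5%, against a target of 1 − 0.95 × 0.80 = 24.0%. At u = 30% the AE-driven value is above the same target. Hospitalisation or death alone would be 5%.

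**Step 4. Who is affected**

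SAP section 2 reports no Cohort 3 participants and a full analysis set of 46. The Cohort 2 count is not given. The planned minimum in protocol Table 5 was 14 IM + 7 IV = 21. If it were 21, each misclassified child would move the percentage by 1/21 = 4.8 points.

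**The case against.** The best defence is that the SAP sentence counts participants with worsening of COVID-19, and that this phrase governs every component, so an unrelated symptom is already excluded. That would settle it if the sentence stopped there, but it goes on to say how worsening is determined, and that operational rule has no relatedness condition on symptoms. A programmer following it would count them.

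Second, the weekly contact supplies what the AE rule leaves out. This stands in part: it can bring in genuine non-serious worsening. It does not remove the ruled-out AEs, and it supplies no AE date. How symptom severity is graded after baseline in Cohort 2 is also not described; SAP 4.1.6 mentions a symptom screen after Day 1 only for Cohort 1.

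Third, severe outcomes are not lost. This stands. WHO scores of 5 to 9 are hospitalised or ventilated states, so severe cases fall within the hospitalisation component; SAEs are summarised under SAP 4.2.2.1; and COVID-19-related death is tabulated under SAP 4.2.5.3. The complaint is that the progression figure cannot be separated into its parts. Including symptom worsening at all in mild to moderate disease is a legitimate design choice.

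A reader might go further and infer that the endpoint fails to mirror the adult one. The documents do not establish that. Protocol 2.3.2 reports one adult result in a benefit section, and no adult definition of progression is supplied. What can be said is that the SAP definition is broader than severe COVID-19 or death, which sits uneasily with the statement in protocol 4.2.1.

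**Conclusion.** The point holds as misclassification. Read together, SAP 4.2.5.2 and protocol 8.1.1 admit symptoms judged not to be COVID-19 and leave genuine non-serious worsening without a usable date. The pooled count also hides how much is mild symptoms and how much is hospitalisation or death.

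A reader might infer that the reported proportion is simply inflated, or dominated by the ordinary course of mild illness. Neither is supported without qualification. If either source counts, the proportion cannot fall below COVID-19-related worsening as the weekly contact captures it, and it will exceed hospitalisation or death alone whenever a child qualifies only on symptoms. If the count is AE-driven, as the date formula suggests, it may be too low. The documents give no symptom rates, so no size can be put on the error; the percentages in the table only show that both directions are possible.

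The consequence is limited. This is a descriptive secondary endpoint, with no hypothesis test, in Cohort 2 only. In a small uncontrolled cohort, though, a few misclassified children would visibly change the percentage.

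**What to change.** Amend SAP 4.2.5.2 as follows.

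- **Exclude ruled-out AEs.** Do not count Table 13 symptom AEs that are non-serious and did not lead to study discontinuation; by protocol 8.1.1 these were judged not COVID-19 related. Also exclude any serious or discontinuing symptom AE recorded as not COVID-19 related.
- **Source and date.** Take non-serious COVID-19 symptom worsening from the weekly contact, and date it by that contact or by symptom onset instead of by an AE date.
- **Separate rows through Day 29.** Report new or worse COVID-19 symptoms, COVID-19 hospitalisation, severe COVID-19 per protocol 8.1.2, and COVID-19-related death, plus a combined row for severe COVID-19 or COVID-19-related death.

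The cost is SAP wording, a small derivation and a few table rows. Seriousness and withdrawal due to the AE are collected for every AE (protocol 8.3.2), so the main exclusion needs no new field. Severe COVID-19 is already an SAE, and COVID-19 deaths are identified on the death form (SAP 4.2.5.3). One limit should be stated: AE causality is collected against the IMP, and for SAEs also against other medication and study procedures (protocol 8.3.2 and 8.3.3). No field for COVID-19 relatedness of a symptom AE is described, so the exclusion of serious or discontinuing unrelated symptoms depends on that judgement having been recorded.

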##### **4.2.5.3 COVID-19-related death**

To evaluate COVID-19-related death through 90 days after a single IM or IV dose of AZD7442 in pediatric participants, the incidence of COVID-19-related death occurring after dosing with IMP up to study day 90 will be tabulated by cohort, weight categories, dose, and route of administration for the SAF.

All fatal events will be further assessed as part of safety evaluation. Identification of deaths related to COVID-19 will be done based on the investigator's judgement and captured in the death details eCRF.

The time to death [date of death – date of Day 1 +1] will also be listed and summarized via n, median, 1st and 3rd quartile, minimum, and maximum by weight categories, dose, and route of administration for the SAF.

#### **4.2.6 Secondary Endpoint – Cohort 3 (Severe COVID-19)**

##### **4.2.6.1 Recovery**

To evaluate the time to sustained recovery from severe COVID-19 after a single IM or IV dose of AZD7442 in pediatric participants, the time from Day 1 to discharge from the index hospital, if and only if followed by being alive and home for 14 consecutive days, will be calculated. In case of multiple discharges due to re-hospitalization, only the first sustained recovery will be considered.

The time to sustained recovery will then be calculated as [date of discharge +14 days – date of Day 1 +1].

The time to sustained recovery will be listed and summarized via n, median, 1st and 3rd quartile, minimum, and maximum by weight categories, dose, and route of administration for the SAF.

#### **4.2.7 Exploratory Endpoint**

To evaluate the concentrations of AZD7442 in nasal fluid after a single IM or IV dose in pediatric participants, nasal concentrations of AZD7442 for each visit will be listed and summarized quantitatively by cohort, route of administration and weight category (1 to 4 and all) for the SAF.

#### **4.2.8 Other Endpoints**

##### **4.2.8.1 Exposure**

The IMP administration dates and times will be listed for each participant together with route of administration (IM or IV), planned dose, administered dose and any medication errors that might occur during administration, such as interruptions.

The listing will be created for the SAF.

##### **4.2.8.2 Injection/Infusion site Inspection**

The results of the inspection of the injection/infusions site will be listed for each participant presenting time of inspection, visual inspection of site, palpation of site, experience of discomfort and change in experience of discomfort. The results will be tabulated qualitatively by route of administration for the SAF.

#### 4.2.8.3 Potential Hy's Law

In case of potential Hy's Law, any liver risk factors, liver signs and symptoms and liver diagnostic investigation information will be listed.

## 5 INTERIM ANALYSIS

For interim analysis, a subset of the above analyses will be performed on all available data at time of the data snapshot. A database lock will be performed and all data cleaned for the data cut.

The interim analysis will include listings, tables and figures including: an overview over the patient population (disposition, demographics, baseline characteristics, medical history), important protocol deviations, safety information (adverse events, COVID related deaths, safety assessments, vital signs), as well as ADA and serum PK concentrations of AZD7442 combined and its individual components and summaries of COVID-19 symptoms and infections, as data permits. Select data may also be presented by cohort, route of administration, weight categories or age groups.

The exact subset of the result tables, listings and figures generated for the interim analysis will be specified in the mock shells.

## 6 APPENDICES

**Table 5 Description of the studies to be included in the population PK analysis.**

Study description	Dose & PK sampling	Number of Subjects in PK dataset	Phase of Study and Study Population
D8850C00001 A Phase I Double-blind, Placebo-controlled Study to Evaluate the Safety, Tolerability and Pharmacokinetics of AZD7442 in Healthy Adults.	Dose: 300 mg IM, 300 mg IV, 1000 mg IV, 3000 mg IV, 3000 mg IV –co-administration PK timepoints: 0, 8 hr, 24 hr, 3, 5, 7, 14, 30, 60, 90, 150, 210, 270, and 360 days post-dose for IM route for both AZD8895 and AZD1061 0, 0.25h, 0.5h, 0.75h, 1h, 8 hr, 24h, 3, 5, 7, 14, 30, 60, 90, 150, 210, 270, and 360 days post-dose for IV route (AZD8895) 0, 0.75h, 1.5h, 2.25h, 3h, 8 hr, 24 hr, 3, 5, 7, 14, 30, 60, 90, 150, 210, 270, and 360 days post-dose for IV route (AZD1061)	50	Phase I, healthy subjects
D8850C00002 A Phase III Randomized, Double-blind, Placebo-controlled, Multi-centre Study in Adults to Determine the Safety and Efficacy of AZD7442, a Combination Product of Two Monoclonal Antibodies	300 mg IM: PK samples collected on 0, 7, 28, 57, 91, 182, and 365 days post-dose	~3333	Phase III, pre-exposure prophylaxis of COVID-19 in Adults

Study description	Dose & PK sampling	Number of Subjects in PK dataset	Phase of Study and Population
(AZD8895 and AZD1061), for Pre-exposure Prophylaxis of COVID-19.			
D8850C00003 A Phase III Randomized, Double-blind, Placebo-controlled, Multi-centre Study in Adults to Determine the Safety and Efficacy of AZD7442, a Combination Product of Two Monoclonal Antibodies (AZD8895 and AZD1061), for Post-exposure Prophylaxis of COVID-19	300 mg IM: PK samples collected on 0, 2, 5, , 14, 28, 57, 91, 182, and 365 days post-dose	~750	Phase III, Potential - exposure (within 8 days) to SARS-COV-2 in Adults
D8851C00001 A Phase III Randomized, Double-blind, Placebo-controlled, Multi-centre Study to Determine the Safety and Efficacy of AZD7442 for the Treatment of COVID-19 in Non-hospitalized Adults	600 mg IM: PK samples collected on 0, 2, 5, 7, 14, 28, 58, 84, 92, 168, 365 days post-dose	~850	Phase III, Treatment of COVID-19 in non-hospitalized Adults
ACTIV-3 A Multicenter, Adaptive, Randomized, Blinded Controlled Trial of the Safety and Efficacy of Investigational Therapeutics for Hospitalized Patients with COVID-19 (NIH funded)	600 mg IV: PK samples collected on Days 0, 5, 28, and 90		Phase II and III, Treatment of COVID-19 in hospitalized Adults
D8850C00006 Open-label, Uncontrolled, Single dose Study to Evaluate the Pharmacokinetics, Pharmacodynamics, and Safety of AZD7442 in Pediatric Participants Aged $\geq$ 29 Weeks Gestational Age to < 18 Years	IM and IV; dose is dependent on cohort indication and participant's weight. PK samples collected at end of infusion (IV only), on either 3, 7, 10 or 14 days post-dose, and then 28, 91, 182, and 365 days post-dose	~100 a	Phase I, pre-exposure prophylaxis, Treatment of COVID-19 in non-hospitalized participants, Treatment of COVID-19 in hospitalized participants

a The enrolment for this study was stopped early due to FDA feedback, therefore the full analysis set will only contain 46 participants.

